#### Remedial Action(s) Taken

The remedial actions taken in response to an adverse event are to be recorded in the medical record. The options included but not limited to the following:

No action taken

Study drug permanently discontinued due to this adverse event

Study drug temporarily interrupted

#### 10.4. Serious adverse events

A serious adverse event is defined in general as an untoward (unfavorable) adverse event which:

- is fatal or life-threatening;
- requires or prolongs hospitalization;
- is significantly or permanently disabling or incapacitating;
- constitutes a congenital anomaly or a birth defect; or
- may jeopardize the patient and may require medical or surgical intervention to prevent one of the outcomes listed above.

Hospitalizations occurring under the following circumstances are not considered serious adverse events:

Admission to a hospice for respite care;

Hospitalizations planned before entry into the clinical study;

Hospitalization for elective treatment of a condition unrelated to the studied indication or its treatment;

Hospitalization on an emergency, outpatient basis that does not result in admission (unless fulfilling the criteria above);

Hospitalization as part of the normal treatment or monitoring of the studied indication;

Hospitalization to facilitate the work up of a ≤ Grade 2 adverse event, including overnight hospitalization following study drug administration for non-medical reasons.

## **10.5. Notification of serious adverse events**

### **10.5.1. Reporting responsibility**

Any serious adverse event occurring in a patient after he/she has provided informed consent, and while receiving study treatment must be reported. All patients who withdraw from the study should be monitored for at least 28 days following the last dose of IP for the occurrence of serious adverse events considered by the Investigator to be related to IP treatment. Patients should be contacted at least once within 28 days following the last dose of IP. Telephone contact is acceptable and should be within ±10 days of the 28-day time point. After 28 days following the last dose of IP, any serious adverse events considered by the Investigator to be related to IP treatment must also be reported. The timeframe for reporting after discontinuation of study drug may be extended if there is a strong suspicion that the IP has not yet been eliminated or the pharmacodynamic effects of the IP persist beyond 28 days. All serious adverse events must also be reported for the timeframe in which the study drug interferes with the standard medical treatment given to a patient.

Each serious adverse event must be reported by the Investigator to the Medical Monitor or its, or designee, within 24 hours of learning of its occurrence, even if it is not felt be related to IP. Serious adverse events occurring after 28 days from the last dose of IP must be reported if deemed related to IP. The report must include the adverse event term, patient identifier, attribution, description, concomitant medications used to treat the adverse event, and any other relevant information. Follow-up information about a previously reported serious adverse event must also be reported to the Sponsor or its designee within 24 hours of receiving the information.

The Sponsor, or its designee, may contact the Investigator to obtain further information about a reported serious adverse event. If warranted, an Investigator Alert may be issued to inform all Investigators involved in any study with the same IP that a serious adverse event has been reported.

#### **10.5.2. Reporting procedures**

The Investigator must complete the Serious Adverse Event Report Form in English, assess the causal relationship to study drug, and send the completed form to the **SAE Reporting FAX Number** within 24 hours, to the Sponsor or its designee. The Medical Monitor will review the Serious Adverse Event Report Form and the supporting source documents during monitoring visits. Follow-up information should also be sent to the Medical Monitor that receives the original Serious Adverse Event Form, within 24 hours of the time the information is known. Either a new Serious Adverse Event Report Form is faxed (indicating that the information is a follow-up), or the original form may be re-faxed (with the new information highlighted and a new date provided). The follow-up report should describe whether the serious adverse event has resolved or is continuing, if and how it was treated, and whether the patient continued or permanently discontinued study participation. The form(s) and FAX confirmation sheet(s) must be retained in the investigational site study file.

The Investigator is responsible for informing the Institutional Review Board/Independent Ethics Committee (IRB/IEC) of the serious adverse event and providing them with all relevant initial and follow-up information about the event. The Sponsor or its designee will communicate serious adverse events to the study sites as required by local regulatory authorities.

#### **10.5.3. Contact persons and numbers**

The contact person and the phone/fax number are listed on the cover page of this protocol.

### **10.6. Overdose**

An overdose is defined as the accidental or intentional ingestion/infusion of any excessive dose of a product. For reporting purposes, the Sponsor considers an overdose, regardless of adverse outcome, as a serious adverse event in Section 10.4

## **10.7. Pregnancy**

Pregnancy testing must be performed in all women with childbearing potential (WWCBP) throughout the study as specified in the Time and Event Schedule table, and the results of all pregnancy tests (positive or negative) are to be recorded on the CRF. All WWCBP must have a negative serum pregnancy test in the screening period and negative urine pregnancy tests during the study. If the pregnancy test is positive, the patient must not receive IP and must not continue in the study. The patient will be followed to determine the outcome of the pregnancy.

In addition, all WWCBP should be instructed to contact the Investigator immediately if they suspect that they might be pregnant (e.g., missed or late menstrual period) at any time in the study period or during the 28-day period following their last dose of study drug.

Male patients should contact the Investigator immediately if they suspect they may have fathered a child during the study or during the 28-day period following their last dose of study drug. When possible, such pregnancies should be followed (to term) to determine the outcome.

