## **7. STUDY SCHEDULES AND PROCEDURES**

The study of each patient is divided into three periods: screening, treatment and follow-up.

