### 7.3. Follow-up period

After completion of the Treatment period, the patients will have 6 monthly follow-up visits. All patients should complete Follow-up Visit 1 ( $28 \pm 3$  days after the last dose of IP).

The procedures for the follow-up visits are as follows:

1. Physical examination
2. Vital signs
3. ECOG performance status
4. AE assessment
5. 12-lead ECG
6. CBC with differentials and D-dimer
7. Coagulation profile: PT, INR, aPTT
8. Blood chemistry profile: fasting glucose, BUN, creatinine, alkaline phosphatase, ALT, AST, total bilirubin, total protein, albumin, globulin, sodium, potassium, chloride, calcium, magnesium, phosphorus, uric acid, lactate dehydrogenase, IgG and IgM.
9. Thyroid function tests: TSH, T3 and free T4.
10. Urinalysis.
11. Urine pregnancy test for female patients with child-bearing potential
12. Concomitant medications
13. Tumor assessment: if the prior imaging studies are done more than 8 weeks ago)
14. Pharmacokinetic and pharmacodynamic studies.

If the patient refuses or is unable to attend the follow-up visit 1, the reason(s) should be noted in the patient's source documentation.

---

 Every 8 weeks.

 A positive urine pregnancy test needs to be verified by a serum beta-HCG test. Postmenopausal women must be amenorrheic for at least 12 months in order not to be considered of child-bearing potential.

 Only for follow-up visit 1.

Completion of subsequent follow-up visits (Follow-up Visits 2 and beyond) will depend on the status of the patients at the end of treatment. Except for patients who discontinue due to worsening PD, all patients will be followed from the last dose of IP for approximately 6 months until relapse, initiation of a new therapy or the toxicities stabilized or  $\leq$  grade 1. The evaluations performed during the Follow-up Visits will be recorded on the CRF.

Whether or not each patient completes the study drug treatment through the first cycle will be documented on the CRF, including how many doses in Cycle 1 were received. Patients will be considered to have completed Cycle 1 treatment if they completed 4 infusions of IP in Cycle 1 and completed all evaluations at the end of Cycle 1.

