### **7.3.1. Survival follow up**

Following completion of the treatment and follow-up periods, all patients will be followed for survival after completion of treatment phases and through the follow-up period of the protocol. Patients will have their survival status assessed approximately every 3 months by either a telephone or in-person contact until study completion or termination by the Sponsor.

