### **7.5.3. Effective contraceptive measures**

For female patients of child-bearing potential and male patients whose sexual partners are of child-bearing potential, patients should agree to use an effective method of contraception during the treatment period and for at least 180 days following the last dose of study drugs.

Effective contraceptive measures include: (a) intrauterine device plus one barrier method; (b) oral, implantable or injectable contraceptive plus one barrier method; or (c) tow barrier methods. Effective barrier methods are male or female condoms, diaphragms, and spermicides (cream or gel that contain a chemical to kill sperms).

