### **10.7.1. Reporting of pregnancy**

Initial information on a pregnancy (during or after the study as defined above) must be reported immediately to Sponsor and the outcome information provided once the outcome is known. The Serious Adverse Event Form must be faxed to the Sponsor or its designee according to Serious Adverse Event reporting procedures described in Section 10.4. A separated Pregnancy notification worksheet in Appendix 15.7 should also be filed to the Sponsor or its designee.

For female patients, protocol-required procedures for study discontinuation and follow-up must be performed unless contraindicated by pregnancy (e.g., x-ray studies, CT scan). Other appropriate pregnancy follow-up procedures should be considered if indicated. Follow-up information regarding the course of the pregnancy, including perinatal and neonatal outcome must be reported. Infants should be followed for a minimum of 8 weeks.

For male patients, follow-up information regarding the course of the partner's pregnancy, including perinatal and neonatal outcome should be reported when possible.

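### Contraception is required to day 180 after the last dose, but for patients who leave follow-up early the duty to notify a pregnancy after day 28 is ambiguous

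*Combined protocol and SAP*

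**What the plan says.** Section 7.5.3 asks women of child-bearing potential, and men whose partners are, to use contraception "during the treatment period and for at least 180 days following the last dose of study drugs".

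Section 10.7 sets the notification duty. Women are to contact the investigator if they suspect a pregnancy "at any time in the study period or during the 28-day period following their last dose of study drug". Men are to do so "if they suspect they may have fathered a child during the study or during the 28-day period following their last dose of study drug". Section 10.7.1 passes this on to the sponsor without adding a later window: "Initial information on a pregnancy (during or after the study as defined above) must be reported immediately to Sponsor".

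Neither the study period nor the study is defined in 10.7. Section 7 says: "The study of each patient is divided into three periods: screening, treatment and follow-up". Section 7.3 plans six monthly follow-up visits, with a urine pregnancy test among the procedures, and expects Visit 1 (day 28 ± 3) of everyone. Later visits do not apply to all: "Except for patients who discontinue due to worsening PD, all patients will be followed from the last dose of IP for approximately 6 months", and for those who do continue, follow-up lasts "until relapse, initiation of a new therapy or the toxicities stabilized" or are grade 1 or lower.

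Section 7.3.1 then adds contacts about every three months: "Following completion of the treatment and follow-up periods, all patients will be followed for survival". The only item it lists for these contacts is survival status.

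**The concern.** The sponsor considers exposure relevant enough to ask for contraception for 180 days, but the only explicit post-dose window for telling anyone about a pregnancy is 28 days. The two periods should match, or the text should say why they do not.

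The patients affected are those who leave follow-up early. Progression is a mandatory reason to stop treatment (Section 7.2.5), and the population is refractory to standard therapy, so leaving for progressive disease is an ordinary route out of the trial. These patients also lose the follow-up pregnancy tests, which leaves their own notification as the main way a pregnancy would come to light.

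This is a first-in-human study with no prior human safety data (Section 1.3.1). Section 10.7.1 requires perinatal and neonatal outcome for female patients and at least 8 weeks of infant follow-up, but that depends on the pregnancy being notified. At stake is an exposed pregnancy, conceived while contraception was still required, that is neither reported nor followed to outcome.

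**Working it through.** The plan gives no figure of its own to reproduce. The check is a cross-reading plus day counts from the last dose.

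**Inputs.** Contraception to day 180 (7.5.3). Explicit notification window to day 28 (10.7). Visit 1 at day 28 ± 3, so day 31 at the latest, and six monthly visits (7.3). All SAEs collected for 70 days after dosing stops (11.3.5.1).

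**Step 1: patients who complete follow-up.** Section 7 makes follow-up part of each patient's study, so the duty in 10.7 runs while they attend. Assuming that a month means between 28 days and a calendar month, six visits end between 6 × 28 = day 168 and 6 × 30.4 = about day 182. The shortfall against day 180 is 180 − 168 = 12 days at most, and none at the other end.

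**Step 2: patients who leave early.** If the last day in follow-up is day L (28 or later), the interval in doubt is 180 − L.
- Leaving by day 28: 180 − 28 = 152 days, which is 152/180 = 84% of the contraception period.
- Leaving at Visit 1 on its latest day: 180 − 31 = 149 days.
- Illustration, leaving at the third monthly visit (3 × 28 = day 84): 180 − 84 = 96 days.

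The documents do not give the share who leave early or when they leave.

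**Step 3: is the duty absent, or only unclear?**
- Pointing to an end at day 28: Section 7.3.1 starts the survival contacts after the treatment and follow-up periods, and footnote 7 of the schedule in Section 14 places them after the follow-up visits. If the study period always ran through survival contacts, the separate 28-day clause in 10.7 would do almost no work.
- Pointing to a continuing duty: 7.3.1 is numbered inside 7.3, and the schedule marks survival status in the follow-up column. Survival follow-up covers all patients until study completion or termination.

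The two sets of text cannot both govern. The duty is therefore ambiguous, not shown to be absent.

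**Step 4: what the SAE rules catch.** Of the 152 days, 70 − 28 = 42 fall inside the 70-day SAE window and 180 − 70 = 110 fall beyond it (42 + 110 = 152). Assuming about 266 days from conception to term, conception on days 29 to 180 leads to birth at about day 29 + 266 = 295 to day 180 + 266 = 446, all well after day 70. A birth defect would then reach the sponsor under 10.4 and 10.5.1 only if the investigator learned of it and judged it related to HLX06. An uncomplicated pregnancy would not be captured.

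**The case against.** The strongest objection is that survival follow-up may be part of the study period. On that reading a woman who stopped for progression must still notify, and a man is still within the study. It does not help to answer that survival contacts ask only about survival, because the duty rests on being in the study and not on being asked. This stands to the extent set out above: a reader might infer that early leavers certainly have no duty after day 28, and the documents do not support that.

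A reader might also infer that no patient has a duty after day 28. That fails, because Section 7 counts follow-up as part of the study.

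Section 7.2.5 says that all who discontinue should comply with follow-up procedures, with withdrawn consent or lost ability to consent as the only exception. This sits uneasily with the progression exception in 7.3. It can, however, be read as sending patients to 7.3 with that exception included, so it adds to the ambiguity without resolving it.

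The instruction to patients would naturally also appear in the consent form, which was not available, nor was the pregnancy worksheet. Either may state a longer window.

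Finally, drug-related SAEs, including congenital anomalies, remain reportable after day 28 with no end date. A reader might infer that adverse outcomes would go wholly unreported; they would not. This backstop is partial, because it does not capture the pregnancy itself.

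**Conclusion.** The mismatch between 180 and 28 days is plain in the text. Its consequence is narrower: for patients who leave follow-up early, the protocol does not settle whether a pregnancy must be notified after day 28. The interval in doubt is at most 152 days, shorter for those who leave later, and about 0 to 12 days for those who complete follow-up.

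In practice the effect is small. At most 30 patients are planned, plus replacements, all asked to use contraception if relevant. The documents give no pregnancy rate, but the expected number is very low. Dose finding and the MTD are unaffected. This is a minor safety correction, worth making because it is cheap.

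The conclusion rests on the visible text of 10.7, 10.7.1 and the sections cited. The day counts for completers and for birth timing rest on the assumptions stated with them.

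**What to change.** In both sentences of 10.7, require notification of any pregnancy, in the patient or a male patient's partner, conceived during treatment or within 180 days after the last dose. The duty should apply whenever the pregnancy is recognised and whether or not the patient still attends visits, unless consent is withdrawn.

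In 10.7.1, state that such pregnancies are reported to the sponsor and followed to outcome, keeping the existing infant follow-up of at least 8 weeks and with no cap at day 180. For partners of male patients this applies when possible, as now.

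Simply replacing 28 with 180 is not enough. The women's window is timed by suspicion, so a conception near day 180 would be suspected only after the window closed. Timing the duty by conception removes both the 152-day interval and that residue.

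Optionally, ask about pregnancy at the existing three-monthly survival contacts.

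The cost is a wording change in two sections, a few more reports and outcome follow-ups (some in patients who no longer attend visits), and an update of the consent form if it repeats the 28-day window. No new visit or test is needed.

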### **10.7.1. Reporting of pregnancy**

Initial information on a pregnancy (during or after the study as defined above) must be reported immediately to Sponsor and the outcome information provided once the outcome is known. The Serious Adverse Event Form must be faxed to the Sponsor or its designee according to Serious Adverse Event reporting procedures described in Section 10.4. A separated Pregnancy notification worksheet in Appendix 15.7 should also be filed to the Sponsor or its designee.

For female patients, protocol-required procedures for study discontinuation and follow-up must be performed unless contraindicated by pregnancy (e.g., x-ray studies, CT scan). Other appropriate pregnancy follow-up procedures should be considered if indicated. Follow-up information regarding the course of the pregnancy, including perinatal and neonatal outcome must be reported. Infants should be followed for a minimum of 8 weeks.

For male patients, follow-up information regarding the course of the partner's pregnancy, including perinatal and neonatal outcome should be reported when possible.

## **10.8. Rapid notification of adverse events of significance**

In addition to serious adverse events, the following adverse events will be reported within 24 hours using the same rapid notification procedures that are used for serious adverse events (described in Section 10.5), even if the nature of the adverse event is not deemed serious:

Adverse events that potentially meet DLT criteria.

Adverse events that potentially meet the delayed DLT criteria.

Grade 3 or 4 infusion reactions whether or not the event is a DLT.

### **10.9. Other safety considerations**

Any significant worsening noted during interim or final physical examinations, electrocardiograms, x-rays, and any other potential safety assessments, whether or not these procedures are required by the protocol, should also be recorded as a non-serious or serious AE, as appropriate, and reported accordingly.

## 11. DESCRIPTION OF STATISTICAL METHODS

### 11.1. Bayesian optimal interval design and sample size determination

We will employ the Bayesian optimal interval (BOIN) design (Liu and Yuan, 2015) to find the MTD. The BOIN design is a novel Bayesian dose-finding method that optimizes patient ethics by minimizing the chance of exposing patients to sub-therapeutic and overly toxic doses. The BOIN design yields an average performance comparable to that of the continual reassessment method (CRM) in terms of selecting the MTD, but has a lower risk of assigning patients to sub-therapeutic or overly toxic doses (i.e., better patient ethics).

The target toxicity rate for the MTD is 0.3 and the maximum sample size is 30. We will enroll and treat patients in cohorts of size 3. But in this study, there are two early stopping rules: (1) when the lowest dose level is eliminated due to toxicity and (2) when the new patient number at certain dose level reaches 15.

The dose escalation/de-escalation rules have been described in the Synopsis and tabulated in Table 1. The R codes used in the BOIN 2.4 package to derive the rules are listed in Section 15.5.

#### 11.1.1.Determination of MTD

After the trial is completed, we determine the MTD based on the isotonic regression as specified in Yuan et al[5].The MTD will be determined by the number of patients with DLT in the first cycle and the total number of patients treated at certain dose level. The BOIN package in R will be used to estimate MTD. The determined MTD is the dose for which the isotonic estimate of the toxicity rate is closest to the target toxicity rate of 30%. If there are ties, we select the higher dose level when the isotonic estimate is lower than the target toxicity rate; and we select the lower dose level when the isotonic estimate is greater than the target toxicity rate.

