**Target toxicity rate: 30%**

**Study cycle: Every four weeks.**

**ATD phase and cohort size**

The accelerated phase starts with one new patient per cohort. When the patient does not experience dose-limiting toxicities (defined later) during the first cycle of treatment at the assigned dose level, the next new patient will be assigned to the next higher dose level of HLX06 (*ie. intrapatient dose escalation is NOT allowed*).

When the first instance of first-cycle dose-limiting toxicities (DLTs), or the second instance of first-cycle grade $\geq 2$  toxicities of any types occurs, the acceleration phase stops and the cohort expands to **three** new patients at the current and subsequent dose levels and switch to BOIN design.

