**Table 1. Dose escalation table**

No. of patients treated at current dose level	3	6	9	12	15
Escalate if # of DLT	0	1	2	3	3
Remain at the same dose if # of DLT	1	2	3	4	4,5
De-escalate if # of DLT	2	3	4	5	6
Eliminate if # of DLT	3	4	6	7	8

The rules to escalate or de-escalate are as follows:

- (a) “Eliminate” means that we eliminate the current and higher doses from the trial to prevent treating any future patients at these doses because they are overly toxic.
- (b) When we eliminate a dose, we automatically de-escalate the dose to the next lower level. When the lowest dose is eliminated, we stop the trial for safety. In this case, no dose should be selected as the MTD.
- (c) If none of the actions (i.e., escalation, de-escalation or elimination) is triggered, we treat the new patients at the current dose.
- (d) If the current dose is the lowest dose and the rule indicates dose de-escalation, we will treat the new patients at the lowest dose unless the number of DLTs reaches the elimination boundary, at which point we will terminate the trial for safety.
- (e) If the current dose is the highest dose and the rule indicates dose escalation, we will treat the new patients at the highest dose up to maximum 30 patients.
- (f) If the number of new patients treated at the current dose reaches 15, stop the trial and determine the MTD based on data from enrolled patients.

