### 1.2. Rationale to develop new anti-VEGFR2 monoclonal antibody

Although ramucirumab has been approved for gastric cancer, its improvement in overall survival is still not satisfactory. It prolongs the overall survival by 6 weeks when combined with paclitaxel. So far, there is not biomarker available to predict the efficacy of ramucirumab.

Therefore, a new monoclonal antibody also targeting VEGFR2 might provide better efficacy for cancer patients.

HLX06 is a new monoclonal antibody targeting VEGFR2. It has better binding affinity to VEGFR2, and also binds to different region in VEGFR2. *In vitro* studies have demonstrated the growth inhibition of human endothelial cells, and HLX06 has shown growth inhibition of tumors in xenogeneic studies.

Nonclinical studies up to weekly 150 mg/kg in *cynomolgus* monkeys for 13 weeks have shown good tolerability without evident toxicities (please refer to Investigator's brochure). HLX06 shows cross-reactivity to both monkey and human VEGFR2, but does not bind rodent VEGFR2.

This study is the first-in-human study to address the safety and tolerability of HLX06 in patients with metastatic or recurrent cancer.

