## **6. ASSESSMENT OF SAFETY AND MANAGEMENT OF TOXICITIES**

### **6.1. Dose limiting toxicities (DLTs)**

DLTs are side effects of a drug or other treatment that are serious enough to prevent an increase in dose or level of that treatment in a clinical study. We use Common Toxicity Criteria for Adverse Events (CTCAE) 4.0 for grading of toxicities in this study.

The definition of DLTs in this study is the toxicities during the first cycle of treatment:

A DLT will be considered to be IP-related unless there is a clear, well-documented, alternative explanation for the toxicity. Delayed DLTs are adverse events that meet the criteria of DLTs that occur after the first cycle of treatment. Delayed DLTs need to be evaluated on a case-by-case basis to make sure that there is no cumulative damage to vital organ function.

Delayed DLTs will also be considered to estimate the MTD for HLX06 in this study.

All adverse events that meet DLT or delayed DLT criteria, as well as any Grade 3 or 4 infusion reactions no matter whether the event is a DLT must be reported to the Sponsor or its designee, within 24 hours.

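### The MTD rule has no 'MTD not reached' outcome, so 0/15 DLTs at 1500 mg would be reported as the MTD although the data exclude a 30% rate

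*Combined protocol and SAP*

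**What the plan says.** Section 11.1 sets the frame: "The target toxicity rate for the MTD is 0.3 and the maximum sample size is 30". Section 11.1.1, repeated in the synopsis, gives the selection rule: "The determined MTD is the dose for which the isotonic estimate of the toxicity rate is closest to the target toxicity rate of 30" per cent. It adds a tie rule: "If there are ties, we select the higher dose level when the isotonic estimate is lower than the target toxicity rate", with the reverse above target. Neither place says how close the estimate must be. The 21%-39% range governs dose moves and the simulations, not the final label.

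The rules under Table 1 cover the two ends of the dose range differently. At the bottom, rule (b) stops the trial if the lowest dose is eliminated: "In this case, no dose should be selected as the MTD". At the top, rule (e) continues treatment at the highest dose when the table signals escalation, and rule (f) stops at 15 new patients and determines the MTD. No text provides for an MTD that was not reached or for a maximum administered dose. RP2D appears only in the abbreviation list.

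Two neighbouring texts matter. In the acceleration phase, after a patient without DLT, "the next new patient will be assigned to the next higher dose level of HLX06"; the phase ends on a first DLT or a second grade 2 or higher event (synopsis; Section 3.1.1), and Table 1 applies after it ends. On the data used, Section 11.1.1 says "The MTD will be determined by the number of patients with DLT in the first cycle", while Section 6.1 says "Delayed DLTs will also be considered to estimate the MTD for HLX06 in this study".

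**The concern.** A closest-to-target rule returns a dose however far the data lie below the target. The plan recognises that the MTD may be unidentifiable at the toxic end but not at the well-tolerated end. The MTD is a primary endpoint (Section 3.5). If the highest dose has a DLT rate clearly below 30%, the correct statement is that the MTD lies above the range studied or was not found. The plan as written would instead report 1500 mg as the MTD, or leave the sponsor to choose another label after seeing the data. The reported simulations do not cover this case: every Table 2 scenario has a dose at or above 30%, and the lowest true rate at level 6 is 45%.

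**Working it through.** **Inputs from the documents.** Target 0.30, maximum 30 patients, cohorts of 3 (Section 11.1); boundaries 0.21 and 0.39 (Section 3.1.2); six levels, highest 1500 mg, start at level 2 (Section 3.2); stop at 15 on a dose (Table 1, rule f).

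**Assumptions.** A dose is eliminated when the posterior probability of a rate above 0.30 exceeds 0.95 under a uniform prior. The documents give no cut-off, and this one gives 5 rather than 6 at n = 9. The Table 2 check starts at level 1, which the documents do not state but which fits the table.

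**1. Reproducing the plan's figures.**
- Escalation boundary: ln(0.79/0.70) / ln[(0.30 × 0.79)/(0.21 × 0.70)] = 0.2532.
- De-escalation boundary: ln(0.70/0.61) / ln[(0.39 × 0.70)/(0.30 × 0.61)] = 0.3441.
- These give the escalate and de-escalate rows of Table 1 exactly; for example, 0.2532 × 15 = 3.80, so escalate at 3 or fewer.
- With 10,000 simulated trials, Table 2 scenario 1 gives 58.4% correct selection and 27.9 patients (stated: 58.5% and 27.7). The selection percentages compared in scenarios 2-5, and early stopping in scenario 6, agree within 2 points.

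**2. Can 15 patients be treated at 1500 mg?** Yes: 4 + 15 = 19 patients with one at each of levels 2-5, or 12 + 15 = 27 with three at each.

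**3. What the rule names.** Take no DLTs at lower doses (1 or 3 patients each). The exact upper limit is the rate p at which P(X ≤ x | 15, p) equals 0.05 (one-sided) or 0.025 (two-sided). For x = 0 this is 1 − 0.05^(1/15) = 0.181 and 1 − 0.025^(1/15) = 0.218.

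| DLTs at 1500 mg | P(this many or fewer) if true rate is 30% | One-sided 95% limit | Two-sided 95% limit | Dose named |
|---|---|---|---|---|
| 0/15 | 0.0047 | 18.1% | 21.8% | 1500 mg |
| 1/15 | 0.035 | 27.9% | 31.9% | 1500 mg |
| 2/15 | 0.127 | 36.3% | 40.5% | 1500 mg |
| 3/15 | 0.297 | 44.0% | 48.1% | 1500 mg |

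If rule (e) is read as allowing up to 30 patients in total, 30 − 4 = 26 could be at 1500 mg. Then 0/26 has a one-sided limit of 1 − 0.05^(1/26) = 10.9%, and 1500 mg is still named.

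**4. How often.** Assume the same true DLT rate at every dose, an accelerated run-in from level 2, and cohorts of three beginning at 1500 mg if no trigger has occurred. The last point is an assumption because the text is silent. There were 4,000 trials per setting; ranges cover a grade 2 rate of 0% or 30%.

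| True DLT rate | 1500 mg named | Named, one-sided limit below 30% | Named, two-sided limit below 30% |
|---|---|---|---|
| 5% | about 99% | 79-80% | 44% |
| 10% | about 94% | 46-47% | 17-18% |

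As a cross-check, with exactly 15 patients at 1500 mg, P(0 or 1 DLT) is 0.95^15 + 15 × 0.05 × 0.95^14 = 0.83 at a 5% rate, and 0.9^15 + 15 × 0.1 × 0.9^14 = 0.55 at 10%. The simulated shares are lower because not every trial takes that path. In the run-in simulation the count at 1500 mg can reach 1 + 5 × 3 = 16, which does not change the conclusion.

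**The case against.** The strongest reply is that this is a labelling gap and no dosing decision changes. The plan defines the MTD as the dose closest to 30%, not as a dose with a 30% rate. Section 3.1.2 treats rates above 30% as undesirable, which makes 30% read like a ceiling. DLTs are listed individually (Section 11.3.5.1), so 0/15 would be visible. Most of this stands: when every dose is below 30%, choosing the top one is what the definition asks for. The 99% and 94% above are therefore not error rates; only the columns in which the limit excludes 30% bear on the point. But a listing does not correct the label on a primary endpoint.

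Three stronger readings are tempting and not supported.

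- A reader might infer that the rule always names a dose. Rule (b) contradicts this, and Table 2 scenario 6 shows 63.7% early stopping.
- A reader might infer that the plan expects a well-tolerated drug. Section 1.2 says nonclinical studies "have shown good tolerability without evident toxicities", but these are monkey data. Section 1.3.1 calls human toxicities unknown and names grade 3 hypertension as the commonest toxicity of the same-target antibody. Low toxicity is plausible; its likelihood is not established.
- A reader might infer that any result in the escalate row of Table 1 (3/15 or fewer) shows that the MTD was not reached. At 2/15 and 3/15 the one-sided limits are 36.3% and 44.0%, and 3/15 or fewer occurs with probability 0.297 when the true rate is exactly 30%.

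**Conclusion.** The point holds in a limited form. The plan has a no-MTD outcome only at the toxic end. If 1500 mg is reached with 0/15 DLTs, it would be reported as the MTD against data that exclude 30% on either limit; at 1/15 the exclusion is one-sided only; at 2/15 there is none. The binomial limits need no assumption beyond independent patients with a common rate. The frequencies (79-80% and 46-47% one-sided; 44% and 17-18% two-sided) rest on assumed flat rates of 5% and 10% and on the assumed handover from titration, and say nothing about how likely those rates are.

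The handover is a separate gap. If 1500 mg is reached without a toxicity trigger, the acceleration rules and Table 1 do not say how one passes to the other. Rule (e) does not clearly settle this because it presupposes a Table 1 signal. How often it would arise depends on toxicity rates that the documents do not give.

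**What to change.** Add to Section 11.1.1 and the synopsis: if the highest dose level is selected and the one-sided 95% exact upper limit for its DLT rate is below 30% (with 15 patients, 0 or 1 DLT), the result is reported as 'MTD not reached; highest dose tested 1500 mg', with the estimated DLT rate and its interval.

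The cost is a less definite primary result when the drug is well tolerated. With 15 patients at a true 30% rate the label would be wrong with probability 0.0047 + 0.0305 = 0.035, about 3.5%. The criterion also needs enough patients: with no DLTs, 0.7^8 = 0.058 and 0.7^9 = 0.040, so it cannot be met with fewer than 9 at 1500 mg. Smaller top-dose groups keep the present label.

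Separately, reconcile the synopsis and Section 3.1.1 with Table 1 on how titration passes to Table 1 if no trigger occurs by 1500 mg, and rule (e) with rule (f) on how many patients may be treated there. Sections 6.1 and 11.1.1 should also agree on which DLTs count, so that the MTD estimate and the new limit use the same numerator.
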